2.1. Schema

- Patients with unresectable advanced or recurrent gastric cancer.
- Patients who are diagnosed as ineffective (intolerant or progression) to standard treatment (first-line or second-line chemotherapy) and have two or more lesions that can be confirmed by imaging.
- 40 cases

Obtaining consent to participate in the trial, checking eligibility criteria, enrolment

Treatment = radiotherapy ➤ Nivolumab (anti-PD-1 Ab)

Radiotherapy: 4.5 Gy once daily for 5 days (total 22.5 Gy/5 times/5 days) to the lesion thought to be the main cause of symptoms if there are symptoms such as pain or paralysis, or to the largest lesion if asymptomatic (second largest lesion if radiotherapy to the largest lesion is difficult). The day that radiotherapy is started is Day 1.

Nivolumab: Dosing is started between Days 15 and 22; Nivolumab is administered at 3 mg/kg (body weight) or 240 mg every 2 weeks for a total of six doses.

End of administration

Follow-up (~Day 180 ± 14) and efficacy assessment (Day 180 ± 14)

End of trial

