If the above criteria are not met, irradiation is postponed on a day-to-day basis until the criteria are met.

Nivolumab (anti-PD-1 Ab) treatment

Dosage and administration

In accordance with the recommended treatment for unresectable advanced or recurrent gastric cancer, 3 mg/kg (body weight) of nivolumab once every two weeks over at least one hour, or 240 mg once every two weeks over at least 30 minutes, is administered via intravenous infusion.

A total of six administered doses is considered the completion of protocol treatment, but there are no specific provisions for treatment after completion.

Continuation of treatment with nivolumab is also permitted within the insurance coverage at the discretion of the attending doctor.

However, any 'unacceptable concomitant or supportive therapy' as defined in 2.4.3) shall be considered a protocol deviation.

Dosing conditions

All of the following conditions should be met when starting administration of this drug.

- 1) White blood cell count \geq 3,000/ μ L and neutrophil count \geq 1,500/ μ L
- 2) Hemoglobin \geq 9.0 g/dL
- 3) Platelets \geq 100,000/ μ L
- 4) Total bilirubin \leq 2.0 times the upper limit of the institutional reference value
- 5) AST (GOT) and ALT (GPT) \leq 3.0 times the upper limit of the facility reference value. (If liver metastases are present, \leq 5.0 times the upper limit of the institutional reference value.)
- 6) Serum creatinine \leq 1.5 times the upper limit of the facility reference value or creatinine - clearance(Ccr) estimate \geq 60 mL/min.

Basis for setting

It is expected that radiotherapy will enhance the efficacy of anti-tumor immunity. We speculate that the use of nivolumab in combination with post-irradiation therapy may induce an abscopal effect in some cases. We decided to start nivolumab between Days 15-22, with Day 1 as the start date of radiotherapy. Because IFN- γ and TNF- α in serum increased about 10-14 days after irradiation (mouse model) (4), and immune responses such as CTL activation were observed about 2 weeks after administration of peptide vaccines and activated dendritic cells (clinical observation).

A possible disadvantage of this treatment strategy is that the combination of radiotherapy and nivolumab may increase or intensify adverse events; however, as far as we have searched, there have been no reports of serious adverse events occurring.

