2.5. Criteria for changes in dosage/use

1) Radiation dose escalation and dose reductions will not be performed. Nivolumab dosage and administration should be in accordance with the recommendations for the treatment of unresectable advanced or recurrent gastric cancer (Appendix).

2) Criteria for discontinuation of treatment

- ① Nivolumab (anti-PD-1 Ab) discontinuation criteria:
 - 1) Failure to meet the criteria for initiation of nivolumab (anti-PD-1 Ab) in '2.3.(2) Nivolumab (anti-PD-1 Ab) treatment' and failure to resume treatment within 14 days of the planned treatment date.
 - 2) If a patient requests discontinuation of nivolumab treatment, irrespective of whether or not it is associated with an adverse event.
 - 3) Death during protocol treatment.
 - 4) Ineligibility due to a known protocol violation, change of pathology diagnosis after enrolment, etc.
 - 5) It is deemed inappropriate to continue treatment due to apparent worsening of clinical symptoms caused by disease progression.
 - 6) Occurrence of Grade 2 or higher interstitial lung disease.
 - 7) Occurrence of Grade 2 or higher eye disorders.
 - 8) Occurrence of Grade 3 or higher bronchospasm, diarrhea, colitis, neurotoxicity, hypersensitivity reactions and injection reactions.
 - 9) Occurrence of Grade 3 or higher thrombocytopenia.
 - 10) Abnormalities in liver function that fulfill one of the following criteria have emerged. AST or ALT $> 5-10$ times the upper limit of the facility reference value for more than 2 weeks.

AST or ALT > 10 times the upper limit of the facility reference value. Total bilirubin levels > 5 times the upper limit of the institutional reference value. Concurrent AST or ALT > 3 times the upper limit of the facility reference value and total bilirubin > 2 times the upper limit of the facility reference value.

11) The principal investigator or a member of research team decides that continued treatment with nivolumab is not appropriate.

② Criteria for discontinuation of radiotherapy

Discontinue radiotherapy if any of the following occur:

- 1) Failure to meet the treatment criteria for radiotherapy in '2.3(2) – Radiotherapy'.
- 2) When the attending doctor decides that discontinuation is necessary due to an adverse event.
- 3) If the patient requests discontinuation of radiotherapy, irrespective of whether or not it is associated with an adverse event.
- 4) Patient deaths.

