- 5) Blood biochemistry: total protein, albumin, total bilirubin, direct bilirubin, AST, ALT, ALP, γ -GTP, BUN, creatinine, LDH, uric acid, CPK, P, Ca, Na, K, Cl, CRP, blood glucose.
- 6) Presence of adverse events (CTCAE v4.0 Japanese translation).
- 7) Immunological parameters.

During nivolumab administration

(After the second dose, assess the following items on the day of administration or the day before administration. Assess following items once from 7 days before to 7 days after the imaging examination date.)

- 1) General findings (temperature, blood pressure, pulse).
- 2) General condition: PS (ECOG).
- 3) Subjective and objective symptoms: fever, nausea, vomiting, diarrhea, decreased appetite, etc. (to be confirmed according to CTCAE v4.0 Japanese translation).
- 4) Blood count (peripheral blood): white blood cell count and fractions, red blood cell count, hemoglobin, MCV, MCH, MCHC, Ht, platelets.
- 5) Blood biochemistry: total protein, albumin, total bilirubin, direct bilirubin, AST, ALT, ALP, γ -GTP, BUN, creatinine, LDH, uric acid, CPK, P, Ca, Na, K, Cl, CRP, blood sugar.
(The following items are only available at the third and sixth doses) RA, ANA, SP-D, KL-6, TSH, free T3, free T4, tumor markers (CEA, CA19-9).
- 6) Contrast-enhanced CT of the chest, abdomen and pelvis (at third and sixth doses). PET-CT is also acceptable. Add MRI if necessary.
- 7) Presence or absence of PD (diagnosed comprehensively based on imaging and clinical findings).
- 8) Presence or absence of adverse events (CTCAE v4.0 Japanese translation).
- 9) Immunological parameters.

During observation

(Assess following items once from 14 days before to 14 days after the 3rd and 6th dose of Nivolumab and Day120.)

- 1) Contrast-enhanced CT of chest, abdomen and pelvis. PET-CT is also acceptable. Add MRI if necessary.

After completion of the protocol

(Assess following items once from 14 days before to 14 days after the Day180.)

- 1) General findings (temperature, blood pressure, pulse).
- 2) General condition: PS (ECOG).
- 3) Subjective and objective symptoms: fever, nausea, vomiting, diarrhea, decreased appetite, etc. (to be confirmed according to CTCAE v4.0 Japanese translation).
- 4) Blood count (peripheral blood): white blood cell count and fractions, red blood cell count, hemoglobin, MCV, MCH, MCHC, Ht, platelets.

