palliative treatment of liver, lung and brain metastases. Radiotherapy is a local treatment and its efficacy in improving prognosis is poor when multiple lesions are present. Although dozens of clinical trials have been conducted on the use of nivolumab in combination with radiotherapy, there are currently no reliable clinical trial reports showing clear efficacy. However, based on basic and translational research reports and case reports, this combination may be expected to activate systemic anti-tumor immunity and enhance the effect of nivolumab and an abscopal effect may be expected to occur in some cases. A possible disadvantage is that the combination of radiotherapy and nivolumab may increase or enhance adverse events. Although serious adverse events, including deaths, have been reported with nivolumab in combination with other therapies, to the best of our knowledge, there are no reports of serious adverse events occurring in combination with radiotherapy. Of course, at present there are no reliable clinical trial reports on the combination of radiotherapy with nivolumab or immune checkpoint inhibitors other than nivolumab, and we need to proceed with this clinical trial carefully.

All treatments used in this clinical trial are covered by health insurance and are carried out as normal insurance treatment, and treatment costs are covered by the health insurance of the research subject and by the research subjects' co-payment. Therefore, the research subjects will not receive any special medical or financial benefits for participating in this clinical trial.

The combination of radiotherapy and nivolumab may increase the respective adverse events or induce unknown adverse events. To minimize the risk or disadvantage of these adverse events, the selection criteria for study subjects, treatment modification criteria, and concomitant therapy are carefully considered. In addition, the attending doctors also medically monitor the adverse events to assess whether they are within the expected range, and take necessary measures in the event of serious or unanticipated adverse events. Furthermore, efforts should be taken to detect these adverse events at an early stage by conducting the tests, etc. defined in '2.7. Observation and examination items'.

13. The status of funding sources for research and the conflicts of interest related to research of the research institution, individual revenues, and attending doctors, etc.

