7.1 Investigation of adverse events

1) Purpose

Examine the occurrence of adverse events to examine the safety of the protocol treatment.

2) Analysis items

Name of adverse event, date of onset, worst grade, severity, outcome, and association with protocol treatment.

3) Analysis methods

The frequency of adverse events occurring from the start date of radiotherapy to the end of study is tabulated by adverse event name and worst grade (toxicity) according to CTCAE ver.4.0, and the Clopper & Pearson two-sided 95% confidence interval is calculated. Calculate the frequency and rate of adverse events, the frequency and rate of adverse events by severity, and the frequency and rate of grade 3 or higher adverse events.

A serious adverse event is defined as having occurred if at least one of the following adverse events is observed, and the frequency and proportion of serious adverse events is calculated.

- ① Death during protocol treatment or within 30 days of last protocol treatment.
- ② Death with undeniable causal relationship to protocol treatment after 31 days of last protocol treatment.
- ③ Grade 4 infection with neutropenia.
- ④ Grade 4 non-hematological toxicity (excluding adverse events in the blood/bone marrow).

Prepare a list of adverse event cases.

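### For patients who complete six nivolumab doses on time, Protocol 2.7 lists no adverse-event review or laboratory assessment between dose six and Day 180, although all adverse events are tabulated to the end of study

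*Protocol*

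**What the plan says.** **Schedule.** Protocol 2.1 fixes the clock: "The day that radiotherapy is started is Day 1". For nivolumab, "Dosing is started between Days 15 and 22", then "every 2 weeks for a total of six doses". Protocol 2.3 treats the sixth dose as completion of protocol treatment, makes no specific provision for what follows, and adds: "Continuation of treatment with nivolumab is also permitted within the insurance coverage at the discretion of the attending doctor".

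**Assessments (Protocol 2.7).** While nivolumab is being given, blood count, biochemistry and adverse events are assessed at the doses. A second sentence in that block ties the items to within 7 days either side of imaging. The block headed 'During observation' says "Assess following items once from 14 days before to 14 days after the 3rd and 6th dose of Nivolumab and Day120" and lists one item: CT or PET-CT, with MRI if needed. The next full list, including laboratory tests and adverse events, is at Day 180 ± 14. Patients who discontinue have a full assessment within 14 days of that decision.

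**Recording and analysis.** Protocol 6.1 requires action on, and CRF recording of, Grade 3 or higher and other clinically significant events up to Day 180. SAP 7.1 is wider: "The frequency of adverse events occurring from the start date of radiotherapy to the end of study is tabulated" by event name and worst grade, with 95% intervals. Protocol 2.6 has the same window and disregards causality. SAP 8.8 lists onset date, worst grade and outcome date for each event. Protocol 12 relies on the 2.7 assessments for early detection: "efforts should be taken to detect these adverse events at an early stage by conducting the tests".

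**The concern.** The analysis promises a complete count of adverse events of every grade, but the data collection behind it changes at dose six. Up to then, events are sought about every 14 days. Afterwards, on the text of 2.7, nothing is scheduled until Day 180, and the Day 120 assessment that falls in between asks only for imaging.

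A single review at Day 180 can recover symptoms that the patient remembers. It cannot recover a symptomless abnormality that came and went, its peak grade, or a reliable onset date. It is not available at all for patients who die first. That matters here because the entry criterion on prognosis asks only for an expected survival of at least 3 months, which is about when dose six is given.

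Any resulting error runs mainly one way, towards under-counting and under-grading. Safety is a named secondary endpoint, and Protocol 12 says that the combination may bring out unknown adverse events. If nivolumab continues in some patients and not in others, the late events also mix two exposure states that SAP 7.1 does not separate.

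**Working it through.** The documents give no figure for this interval, so there is none to reproduce. The check is date arithmetic.

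**Inputs**
- First dose on day *s* = 15 to 22 (Protocol 2.1).
- Six doses at 14-day intervals, so five intervals (Protocol 2.1).
- Closing assessment at Day 180, window Day 166 to 194 (Protocol 2.7).
- End of the adverse-event window taken as Day 180, which Protocol 7 defines as study completion.

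**Dose six** = *s* + 5 × 14
- *s* = 15: Day 85
- *s* = 22: Day 92

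**Gap** = closing assessment − dose six

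| First dose | Dose six | To Day 166 | To Day 180 | To Day 194 |
|---|---|---|---|---|
| Day 15 | Day 85 | 81 | 95 | 109 |
| Day 22 | Day 92 | 74 | 88 | 102 |

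Share of 180 days at the nominal Day 180: 95/180 = 52.8% and 88/180 = 48.9%.

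**What shortens the gap to Day 180**
- *Late sixth-dose imaging.* Imaging 14 days after dose six, with its linked items 7 days later, puts the last review at Day 85 + 21 = 106 or 92 + 21 = 113. The gap is 74 or 67 days (41% or 37%).
- *Dose delays.* Protocol 2.5 stops nivolumab only on "failure to resume treatment within 14 days of the planned treatment date", so delays up to that limit are possible. If every interval runs 7 days late, dose six is Day 15 + 5 × 21 = 120 or 22 + 105 = 127, and the gap is 60 or 53 days. If every interval runs 14 days late, dose six is Day 155 or 162, and the gap is 25 or 18 days.
- *Imaging-linked rule read to cover Day 120.* The nominal gap splits into 120 − 85 = 35 or 120 − 92 = 28 days, then 180 − 120 = 60 days. The longest stretch is 60 days (33%).

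**Do the nivolumab-period rules reach past dose six?** The per-dose rule states no last dose, so it could be read to cover continued nivolumab. Against that, Protocol 2.4 ends protocol treatment after dose six, Protocol 2.3 makes no provision afterwards, and SAP 5.2 summarises dosing only to dose six. SAP 8.6 lists administration dates without saying whether later doses count. The text does not settle the point. For a patient who stops nivolumab at dose six, neither rule clearly applies.

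**The case against.** A reader might infer that about half of the adverse-event window is unmonitored, and that serious toxicity could progress unseen for three months. The documents do not support that. Protocol 6.1 keeps Grade 3 or higher events, and clinically significant events of any grade, under action and CRF recording to Day 180. Protocol 12 has attending doctors monitor adverse events. The Day 180 item has no look-back limit, and patients who discontinue have a full assessment. What is exposed is lower-grade, transient or symptomless events and the accuracy of grades and dates.

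A reader might also infer that several further nivolumab doses would be given with no scheduled safety assessment. That turns an ambiguity into a fact, because the per-dose rule in 2.7 has no stated upper limit.

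Two further objections stand. 'About half' describes on-time completers of six doses only. And the inspection-schedule table in 2.7 is not legible by column in the text available, so a laboratory mark at Day 120 cannot be excluded. If there is one, it disagrees with the written list.

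It can also be said that the intensity of follow-up after protocol treatment is a design choice in a proof-of-concept study. For laboratory monitoring that is accepted, and no such rule is proposed here. It does not answer the mismatch between what is collected and what SAP 7.1 tabulates. Section 6.1 schedules no contact, and its threshold is narrower than the table it would have to feed.

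**Conclusion.** The point holds for patients who complete six doses on schedule. The written lists contain no adverse-event review or laboratory assessment between the sixth-dose assessments and the Day 180 visit. Nominally this is 88 to 95 days (49 to 53% of 180 days), and 74 to 109 days over the Day 180 window. It is shorter with delays or late sixth-dose imaging, and at most 60 nominal days if the imaging-linked rule covers Day 120.

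Late lower-grade events, worst grades and onset dates are liable to be under-recorded, most of all in patients who die before Day 180. The documents give no basis for calculating how many events would be missed. The primary endpoint is unaffected. This is a cheap improvement to a secondary endpoint, not a defect that undermines the trial.

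The conclusion assumes that the end of study for adverse events is Day 180 and that the written lists in 2.7, rather than the table, govern.

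**What to change.** 1. In Protocol 2.7, 'During observation', add two entries to the existing Day 120 imaging assessment: adverse events graded by CTCAE v4.0, and whether nivolumab is continuing. Neither needs a test. For an on-time patient this splits the 88 to 95 days into 28 to 35 days and 60 days.
2. In SAP 7.1, show adverse events by period, up to dose six and after it, with the number of patients still under observation in each period. State how the cut is made for patients who stop before dose six.
3. Reconcile Protocol 2.3, 2.6, 2.7 (text and inspection schedule) and 6.1 with SAP 7.1, so that it is clear whether the per-dose and imaging-linked assessments apply at Day 120 and to doses after the sixth. Which laboratory monitoring should apply is for the investigators to decide.

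The cost is one short CRF entry per patient and a slightly higher reported count of low-grade events.

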2.8. Expected number of cases

40 cases.

Basis for setting

Based on a previous study (ONO-4538-12 study) (5), the disease control rate is set at 40%. At a one-side significance level of 5% and a power of 80%, a sample size of 39 cases are required to detect an additional 20% improvement expected from the study treatment.

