2.2. Research design

Phase I/II, single-arm, open (non-randomized), prospective study

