2.6. Evaluation items

The primary endpoint of this clinical trial is the disease control rate of non-irradiated target lesions, in order to explore the efficacy (additive effect) of radiotherapy to immunotherapy with nivolumab, which is already established as third-line chemotherapy in unresectable advanced or recurrent gastric cancer. Secondary endpoints will also include 1) median survival time (MST) and 2) safety (grade and frequency of adverse events), 3) local control rate (disease control rate of irradiated target lesions), and 4) immunological parameters.

(1) Primary endpoint

Disease control rate

The rate of patients with a best overall response of stable disease (SD) or better confirmed by 180 days, starting from the start date of radiotherapy (Day 1). CT (MRI is also acceptable) and whole-body PET-CT will be used to determine overall response such as complete response (CR), partial response (PR), SD, progressive disease (PD) at each imaging time according to the RECIST Guidelines Version 1.1. If imaging is not available, the patient is considered deficient (NE). CR or PR as the best overall response is defined as two or more consecutive CRs or PRs. If the best overall response does not meet the criteria for CR or PR, and the patient has no PD on the 6th dose of nivolumab and Day 120, the best overall response is considered to be SD. For evaluation, target lesions other than those treated with local radiotherapy are considered as target lesions. If the lesions cannot be evaluated based on the above criteria, they will not be included in the analysis for best overall response.

(2) Secondary endpoint

1) Median survival time (MST)

Overall survival is defined as the period from the start date of radiotherapy until the date of death from any cause. In surviving cases, the last date of confirmation of survival is the date of termination (survival confirmed by telephone contact is acceptable, but confirmation of survival should be recorded in the medical record). Untraceable cases are terminated on the last date of confirmed survival before the loss of follow-up. At the end of the study period, all enrolled cases will be confirmed alive.

2) Safety (grade and frequency of adverse events)

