2.10. Statistical analysis

(1) Statistical analysis of the evaluation

The composition of the population to be analyzed shall be as follows:

- 1) All enrolled cases: the population of enrolled patients, excluding duplicate enrollments and incorrect enrollments.
- 2) All eligible cases: the population excluding ineligible cases (posterior ineligibility, ineligibility at enrollment, offending enrollment) from all enrolled cases.
- 3) Largest analyzed population (FAS): all eligible cases for whom treatment was administered.

(2) Method of analysis

Primary endpoints

- 1) Disease control rate

For FAS cases, summarize the responses of non-irradiated target lesions in a contingency table, and calculate the cumulative disease control rate and the Clopper & Pearson two-side 90% confidence interval. The disease control rate was defined as the total number of patients with CR/PR/SD divided by the number of eligible patients.

Secondary endpoint

- 1) MST

For FAS cases, estimate the MST using the Kaplan-Meier method, along with a two-sided 95% confidence interval using the Brookmeyer-Crowley method.

- 2) Safety

For all enrolled cases, data regarding AEs and toxicities were tabulated, and the Clopper & Pearson two-sided 95% CI was calculated.

- 3) Local control rate

For FAS cases, summarize the responses of irradiated target lesions in a contingency table, and calculate the cumulative disease control rate and the Clopper & Pearson two-side 90% confidence interval. The disease control rate was defined as the total number of patients with CR/PR/SD divided by the number of eligible patients.

- 4) Immunological parameters

Analyzes are performed at Fukushima Medical University Hospital, Kanagawa Cancer Centre,

and by outsourced testing, as appropriate.

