Within 28 days of registration: corticosteroids (excluding temporary use and prednisone or prednisolone equivalent ≤ 15 mg/day), immunosuppressant drugs, anti-cancer drugs, adhesive

treatment of pleura or pericardium, surgery with general anesthesia, and unapproved drugs.

Within 14 days of registration: surgery with local or superficial anesthesia.

12) Participating in other clinical trials or clinical studies (excludes those without intervention).

13) Patients with a positive HIV antigen/Ab test or HTLV-1 Ab test.

14) Patients who have history of treatment using ONO-4538, anti-PD-1 Ab, anti-PD-L1 Ab, anti-PD-L2 Ab, anti-CD137 Ab, anti-CTLA-4 Ab, or other Ab or drug therapies for T-cell regulation.

15) Patients determined by the investigator to be ineligible for participation in this study.

4. The scientific rationale for the research

This clinical trial is designed to investigate the additive effect of nivolumab and radiotherapy in patients with unresectable advanced or recurrent gastric cancer with intolerance or progression after standard treatment (primary and secondary chemotherapy), by administering the insured radiotherapy immediately before nivolumab treatment, a third-line treatment indicated by insurance. The results of basic and preclinical studies, as well as those of case reports, suggest that the combination of radiotherapy and anti-cancer immunotherapy may have a synergistic anti-tumor effect. However, no clinical trials similar to this study have been reported to date in patients with gastric cancer, and this study is a phase I/II clinical study exploring safety, clinical efficacy, and immunological changes of the combination therapy using radiotherapy and nivolumab in patients with unresectable advanced or recurrent gastric cancer. The number of planned cases is considered to be the minimum required for statistical purposes.

5. The procedure for obtaining informed consent

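### Protocol 2.8 claims 80% power with 39 patients, but the planned exact analysis gives 73.5% at 39 and 79.1% at the planned 40

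*Protocol*

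**What the plan says.** The trial is a single-arm study. Protocol 2.8 takes a disease control rate of 40% from a previous nivolumab study, expects a further 20% from the study treatment, and states: "At a one-side significance level of 5% and a power of 80%, a sample size of 39 cases are required". The planned number is 40. No formula or test is named, and the one patient above 39 is not described as an allowance for losses. Section 4 adds: "The number of planned cases is considered to be the minimum required for statistical purposes".

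For the primary endpoint, Protocol 2.10 and SAP 6.1 both say to "calculate the cumulative disease control rate and the Clopper & Pearson two-side 90% confidence interval". Neither document says what result would count as success.

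The analysis set is defined in Protocol 2.10 as "Largest analyzed population (FAS): all eligible cases for whom treatment was administered", so it can be smaller than the number enrolled. The text differs on the denominator. Section 2.6 says: "If the lesions cannot be evaluated based on the above criteria, they will not be included in the analysis for best overall response". Section 2.10 says: "The disease control rate was defined as the total number of patients with CR/PR/SD divided by the number of eligible patients". SAP 6.5 plans no sensitivity analysis for missing values.

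**The concern.** The lower limit of a two-sided 90% Clopper-Pearson interval is an exact one-sided 5% bound, which matches the significance level in 2.8. The natural reading is that this limit will be compared with 40%. The sample size should then deliver its stated power under that exact comparison. An approximate formula need not do so with about 40 patients, because the count is discrete and the exact cut-off moves in whole patients.

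Two things are at stake. The power statement in 2.8 may not be true of the analysis that will be run. And without a written rule, a borderline count could be called positive by one method and negative by the other.

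**Working it through.** **Inputs.** Null rate p0 = 0.40, one-sided alpha 0.05 and target power 0.80, all from Protocol 2.8. Alternative p1 = 0.60, reading the additional 20% as absolute; this reading reproduces 39. Analysis: Clopper-Pearson 90% interval, from Protocol 2.10 and SAP 6.1.

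**Reproducing 39.** With z values 1.645 and 0.842, (1.645 + 0.842)² ≈ 6.183.

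- Normal approximation, variance 0.24: 6.183 × 0.24 / 0.20² = 37.1, so 38.
- Arcsine: 6.183 / (2·asin√0.6 − 2·asin√0.4)² = 38.1, so 39.
- Normal approximation, maximum variance 0.25: 6.183 × 0.25 / 0.20² = 38.6, so 39.

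So 39 is a legitimate result of a standard approximation.

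**Exact power.** For each n, the bar r is the smallest count with P(X ≥ r | 0.40) ≤ 0.05. This is also the smallest count whose Clopper-Pearson 90% lower limit exceeds 40%. Power is P(X ≥ r | 0.60).

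| n | bar | alpha | power |
|---|---|---|---|
| 35 | 20 | 3.0% | 70.0% |
| 36 | 20 | 4.3% | 76.4% |
| 37 | 21 | 2.9% | 71.8% |
| 38 | 21 | 4.1% | 77.8% |
| 39 | 22 | 2.8% | 73.5% |
| 40 | 22 | 3.9% | 79.1% |
| 41 | 23 | 2.7% | 75.0% |
| 42 | 23 | 3.8% | 80.3% |
| 43 | 24 | 2.6% | 76.4% |
| 44 | 24 | 3.6% | 81.4% |

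The smallest n meeting both targets is 42. Power dips below 80% again at 43 and stays above 80% from 44 to 49, the largest size checked.

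**Lowering the bar by one.** At 39, a bar of 21 has 82.9% power, but P(X ≥ 21 | 0.40) = 5.6% and the lower limit for 21/39 is 39.6%, below the null. The limit for 22/39 is 42.1%. At 40, the limits are 38.5% for 21 and 40.9% for 22.

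**Does the result depend on the exact reading?** For a z-test with null standard error √(0.24/n) and critical value 1.645:

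- 21/40: (0.525 − 0.40)/0.0775 = 1.61, not significant. 22/40 gives 1.94. The bar is again 22, so power at 40 is 79.1% under either test.
- 21/39: (0.538 − 0.40)/0.0784 = 1.77, significant. Here the two methods disagree.

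**Non-evaluable patients.** The documents give no rate, so take 1 to 5 of 40 as an assumption.

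- Dropped from the denominator: n = 39 down to 35 in the table, power between 70.0% and 77.8%.
- Kept in a denominator of 40 as not controlled, with 60% holding among the others: P(Bin(40 − k, 0.6) ≥ 22) = 73.5%, 67.0%, 59.7%, 51.8% and 43.6% for k = 1 to 5.
- Kept in, with the 60% already counting them as not controlled: 79.1%.

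**The case against.** The strongest reply is that 39 is not a mistake. A standard formula gives it, 2.8 names no test, and under the matching z-test the bar at 39 is 21, with 82.9% power. That is right as to where 39 comes from: this is a mismatch between an approximate sample-size formula and an exact planned interval, not a slip in arithmetic. It does not rescue the statement. A bar of 21 at 39 has a true alpha of 5.6%, above the stated 5%, and fails the interval that the plan actually specifies.

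It is also fair that 39 sits in a trough of the discrete power curve (38 does better), that 40 is the number planned, and that the gap there is 0.9 points. The trial is presented as an exploratory proof of concept. These points limit the importance. They do not make the sentence in 2.8 correct, since the protocol chose to justify its size by significance level and power.

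Finally, the series falling to 43.6% is not power at a 60% rate over all 40. With 5 non-evaluable patients the overall rate would be 0.60 × 35/40 = 52.5%. That stands: the series shows what the unresolved denominator could cost and is not an estimate of the trial's power. The denominator conflict is an endpoint-definition issue in its own right, but it also decides which power figure applies.

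**Conclusion.** The concern holds and is minor. Under the planned exact interval, 39 patients give 73.5% power, not 80%, and no cut-off at 39 meets both stated targets. The planned 40 gives 79.1% with attained alpha 3.9%, a shortfall of under one point that does not call for more patients.

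The 40-patient figure is the same under the exact and the z-test reading. The 39-patient figure rests on success meaning a lower limit above 40%, which is inferred from the matching one-sided 5% and two-sided 90% levels. All figures take the 20% as absolute. The 70-78% range rests on an assumed loss of 1 to 5 patients from the analysis set. Until 2.6 and 2.10 agree on the denominator, the power for the set actually analysed cannot be stated.

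**What to change.** Do not change enrolment.

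1. **Protocol 2.8:** name the method, remove the claim that 39 gives 80%, and restate along these lines: *With 40 analysed patients, exact power is 79% for a true disease control rate of 60% against 40% (one-sided alpha 3.9%); it is 70-78% if 1 to 5 patients are excluded.*
2. **SAP 6.1:** write the success rule as a Clopper-Pearson 90% lower limit above 40%. That means 22/40 if all 40 are analysed, otherwise the bar for the actual size (22/39, 21/38, 21/37, 20/36 or 20/35). This stops 21/39 from being read both ways.
3. **Protocol 2.6 and 2.10:** reconcile whether non-evaluable patients stay in the denominator, and quote the power on that basis.

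The cost is wording only. The stated power becomes slightly less favourable; enrolment, conduct and the planned interval stay as they are.
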